APPENDIX A: KNOWLEDGE QUESTIONNAIRE

	True	False	Don't Know
1. A sudden cardiac arrest is the same as a myocardial infarction (heart attack).			
2. Conditions that place a person at risk for sudden cardiac arrest include all of the following: history of a heart attack, family history of cardiac arrest, weakened heart muscle.			
3. Ventricular tachycardia and ventricular fibrillation are abnormal heartbeats (rhythms) that can lead to sudden cardiac arrest and possibly death.			
4. Sudden cardiac arrest causes more deaths each year than breast cancer and AIDS combined.			
5. An ICD could save me from sudden cardiac arrest.			
6. If I have an ICD, I no longer have to take my medications.			
7. The ejection fraction is a measure of how fast my heart beats when it is in an abnormal rhythm.			
8. An ejection fraction less than 30% puts me at risk for sudden cardiac arrest			
9. Having an ICD placed requires me to have open-heart surgery.			
10. The ICD procedure carries some risks such as: puncturing a hole in the heart or lung, infection, stroke and bleeding.			
11. Once I have my ICD implanted, I have to avoid strong magnets or metal detectors in airports.			
12. If your heart rhythm is ventricular tachycardia or ventricular fibrillation (abnormal heart rhythms originating from the bottom chambers of the heart), the ICD device should respond with a shock to the heart.			
13. My ICD needs to be checked every 3-6 months to ensure it is working properly and to check the battery status.			

APPENDIX B: DECISIONAL CONFLICT SCALE

Which treatment option do you prefer?

- a. ICD placement with medications
- b. No ICD, continue with medications only
- c. Unsure

Now, thinking about the choice you are about to make/just made, please look at the following comments about your decision regarding placement of an implantable cardioverter defibrillator. Please answer how you feel about these comments by CIRCLING THE RESPONSE that best shows how you feel about the decision you are about to make/have just made.

1. I'm aware of the therapies available to protect me from sudden cardiac arrest.	Strongly agree 0	Agree 1	Neither agree nor disagree 2	Disagree 3	Strongly disagree 4
2. I feel I know the benefits of an ICD.	Strongly agree 0	Agree 1	Neither agree nor disagree 2	Disagree 3	Strongly disagree 4
3. I feel I know the risks and potential complications of having an ICD implanted.	Strongly agree 0	Agree 1	Neither agree nor disagree 2	Disagree 3	Strongly disagree 4
4. I am clear about which benefits of the ICD matter most to me.	Strongly agree 0	Agree 1	Neither agree nor disagree 2	Disagree 3	Strongly disagree 4
5. I am clear about which risks and potential complications of the ICD matter most.	Strongly agree 0	Agree 1	Neither agree nor disagree 2	Disagree 3	Strongly disagree 4
6. I am clear about which is more important to me (the benefits or the risks and potential complications of and ICD)	Strongly agree 0	Agree 1	Neither agree nor disagree 2	Disagree 3	Strongly disagree 4
7. I have enough support from others to make a decision.	Strongly agree 0	Agree 1	Neither agree nor disagree 2	Disagree 3	Strongly disagree 4
8. I am choosing without pressure from others.	Strongly agree 0	Agree 1	Neither agree nor disagree 2	Disagree 3	Strongly disagree 4
9. I have enough advice to make a decision.	Strongly agree 0	Agree 1	Neither agree nor disagree 2	Disagree 3	Strongly disagree 4
10. It's clear what decision is best for me.	Strongly agree 0	Agree 1	Neither agree nor disagree 2	Disagree 3	Strongly disagree 4

11. I feel sure about the decision.	Strongly agree 0	Agree 1	Neither agree nor disagree 2	Disagree 3	Strongly disagree 4
12. This decision is easy for me to make.	Strongly agree 0	Agree 1	Neither agree nor disagree 2	Disagree 3	Strongly disagree 4
13. I feel I have made or will make an informed decision.	Strongly agree 0	Agree 1	Neither agree nor disagree 2	Disagree 3	Strongly disagree 4
14. My decision shows what is most important to me.	Strongly agree 0	Agree 1	Neither agree nor disagree 2	Disagree 3	Strongly disagree 4
15. I expect to stick with my decision.	Strongly agree 0	Agree 1	Neither agree nor disagree 2	Disagree 3	Strongly disagree 4
16. I am satisfied with my decision	Strongly agree 0	Agree 1	Neither agree nor disagree 2	Disagree 3	Strongly disagree 4

APPENDIX C: VIVID QUALITATIVE INTERVIEW GUIDE
APPENDIX D: PROPOSED VIVID CALL CENTER SCRIPT
APPENDIX E: VIVID STUDY INFO SHEET

The above appendices are included separately.

1.1 Primary Objective

VIVID is a prospective randomized controlled clinical trial that will evaluate in black patients:

- Whether a video decision support intervention compared with clinician counseling i.e. usual care (UC), will increase the proportions of patients accepting ICD implantation.

1.2 Secondary Objectives

- Whether the proportions of patients accepting ICD in concordant video group is higher relative to discordant video group.
- To evaluate whether change (i.e. pre to post intervention improvement) in patients' knowledge of SCD and ICDs in the educational video intervention group is larger compared to change in the UC group.
- To evaluate whether change in decisional conflict from baseline to one-week follow up in the educational video intervention group is different than for the UC group. This change will also be evaluated comparing the racially concordant vs. racially discordant video.
- To evaluate whether proportion of patients with an ICD implanted within 90 days of study enrollment in the educational video intervention group is higher compared to the UC group. This proportion will be also evaluated comparing the racially concordant vs. racially discordant video.
- To determine if the time (minutes) spent with the clinician is different in the intervention compared with UC arms.

1.3 Patient Eligibility and Consent

Inclusion criteria:

- 1) Non-hospitalized patients with ejection fraction $\leq 35\%$
- 2) New York Heart Association class I-III heart failure,
- 3) Age >21
- 4) Eligible for an implantable cardioverter defibrillator (ICD) for the primary prevention of sudden cardiac death
- 5) Self-identified race as black
- 6) Provision of informed consent to participate in the study.

[figure not shown]
Exclusion criteria:

- 1) Life expectancy <12 months

- 2) Listed for Orthotopic Heart Transplantation (OHT)
- 3) Transplant (OHT) or OHT imminent within 12 months,
- 4) History of ventricular fibrillation or sustained ventricular tachycardia without reversible causes (secondary prevention indication)
- 5) ICD already implanted (pacemaker upgrade that met other criteria would be eligible)
- 6) Myocardial infarction within the last 40 days,
- 7) Coronary revascularization within the last 3 months,
- 8) Patients who are unable to understand the study procedures due to cognitive or language barriers.
- 9) Inpatients will be excluded from the study because decision-making processes are thought to be appreciably different in inpatients as compared with outpatients.
- 10) Plan a priori for subcutaneous ICD (Sub-Q ICD) (dialysis patients etc..)

1.4 Study Design

Study processes are outlined in Fig. 1.

The Research Assistant (RA) will screen patients for participation/eligibility, prior to the patients scheduled visit to the electrophysiology clinic. When possible an introductory letter will be sent to potential patients by mail from their provider and research team. At the electrophysiology clinic visit, the RA will approach the patient about participation in the study. At that time (baseline visit), the RA will review study procedures and begin the consenting process. The consent process will include a full explanation of the research protocol and aims, as well as use of the iPad technology for the patient to review and sign the consent. The patient will also review and sign a medical release form, to facilitate patient follow-up, if the patient is not

available via phone. In certain U.S. states, the patient will also review and sign a bill of rights statement. Following the consent and other document(s) signature process, the patient will provide baseline demographics (age, gender, payer status, household income, education, distance from health care facility, method of transportation, current employment status and a number of other social determinants), followed by administration of the Health Related Quality of Life Survey (HRQOL) SF-12v2, a depression assessment PHQ- 2, knowledge questionnaire and the decisional conflict scale (DCS), on the iPad. The patient will then be randomized on the iPad to one of the three study arms: A) video with black participants, B) video with white participants, or C) usual care (UC), i.e. clinician counseling. The patient will view a video (per randomization) or consult with their clinician to discuss the ICD procedure. After exposure to their assigned arm (video or usual care), but prior to the conclusion of the visit, patients will be administered on the iPad the same knowledge questionnaire as before the randomization. Using the iPad at the end of the visit, the RA will note the length of time the patient spent with the provider using an iPAD based timer.

Following consent and other processes on the iPad, the RA will collect baseline visit data from the patient's medical record, including medical history, heart failure classification (NYHA), etc. The baseline data will be entered into the Data Collection Form (DCF). For each patient enrolled, the RA will be responsible for submitting the iPad data and entering the baseline visit data via the DCF within a short time.

Following the baseline visit, the DCRI Outcomes Call Center interviewing team will contact patients at two intervals: one-week post intervention and 90-days post-intervention to ascertain information regarding ICD decision/implantation and to administer questionnaire(s). Medical record abstraction will be performed to determine ICD implantation among patients who cannot be reached at 90-days. For those individuals who did not receive an ICD we will seek to understand reasons for no ICD implantation utilizing chart review and telephone interview.

1.5 Sample Size Justification

Note: The primary outcome sample size computations were originally based on two co-primary comparisons (video vs. usual care and concordant vs. discordant video) with the Bonferroni adjustment for type I error by specifying two-tailed 0.025 type I error ($0.025=0.05/2$) for each of the two above comparisons. Due to challenges with enrollment, prior to data lock and unbinding, a single primary comparison of video vs. usual care was chosen and type I error of 0.05 will be used.

The primary outcome is proportions of patients accepting ICD implantation in video vs. usual care (UC) groups at 1 week after baseline visit. The sample size has been determined to provide a reasonable level of confidence for detecting clinically important differences in decision of ICD implantation between groups if such differences indeed exist. *In the pilot study 60% of black patients in the video group indicated yes for ICD placement compared with 43% in the UC arm.* We estimated a 15-20% increase in the proportion of patients indicating yes for ICD implantation in the video group could change practice patterns. Considering the above UC proportion of 43%, with total of 309 analyzable subjects with equal spread into the UC, concordant video, and discordant video groups (i.e. 103 patients in each of the three randomized groups) there is 91% power to detect 20% absolute increase in the combined video group, and 80% power to detect 17% absolute increase.

2. Statistical Analysis

All analyses will be conducted using SAS version 9.4 or higher software (SAS Institute Inc., Cary, NC) and R version 3.5.3 (R Foundation for Statistical Computing, Vienna, Austria). A p-value <0.05 will be considered as statistically significant.

2.1 Demographics and Baseline Characteristics

Frequency distribution and summary statistics for demographic and baseline variables will be presented by educational video and usual care. Continuous variables will be summarized as mean (\pm SD), median and inter-quartiles, categorical variables will be presented as counts and percentages.

2.2 Primary Outcome – ICD acceptance at 7 days in video vs. usual care

The proportions of patients accepting ICD implantation at 7 days between educational video intervention and usual care will be compared. The white ICD educational video (discordant) and black ICD educational video (concordant) will be combined. Pearson chi-square test will be used to test whether there is a difference in the proportion of patients accepting ICD implantation between combined video intervention group and usual care group. We do not expect small counts in light of the pilot study results but, if necessary, the Fisher Exact Test will be used. In addition to a p-value, we will provide the estimate of difference in proportions and 95% confidence interval (CI). **We will also evaluate whether the ICD acceptance treatment effect differed prior to and after introduction of the CMS regulations regarding shared decision process (February 15, 2018).**

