Since there is no existing decisional conflict scale (DCS) for assessing decisional conflict associated with ICD implantation, we have modified a previously validated DCS used for decision-making in breast cancer screening, influenza vaccination, and coronary revascularization procedures. This tool was also developed with the assistance of our patient, provider and general public focus groups and our stakeholder advisory panel. This DCS was tested in our pilot study and performed well. The DCS will measure the effect of the video on decisional conflict and the decision for ICD placement. The overarching goals of the DCS are to assess overall decisional conflict measured through five subscales: 1) informed subscale 2) values clarity subscale, 3) support subscale, 4) uncertainty subscale and 5) effective decision subscale. Prior to the intervention and at 1-week post intervention, participants will be asked to give their decision for ICD implantation (yes, no, unsure) followed by the administration of the DCS. Respondents will be asked to reflect on their decision and respond to the DCS questions using a 5-point Likert scale. Responses to each statement are scored 0 (strongly agree) to 4 (strongly disagree). Total scores range from 0 to 100, with higher scores indicating greater decisional conflict (Appendix B). We will compare the delta change pre to post DCS scores across study arms. To determine the effect of racial concordance between video participants (physicians and patients with ICD's and their families in the video) and study participants we will compare the delta change in pre and post DCS scores, decision for ICD implantation, and ICD receipt within 90 days of the decision in racially concordant intervention compared with racially discordant intervention.

IN-DEPTH INTERVIEW GUIDE

The Round 1 in-depth Interview Guide is designed to elicit patient perspectives on the educational information they received regarding the ICD, including information that was reassuring, concerning, confusing, etc. Patients randomized to a video arm will be asked specific questions about the video component. All patients will be asked questions regarding the conversation they had with their provider. In addition, patients will be asked a series of questions to better understand factors and individuals important to their ICD decision. The guide

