We will conduct Round 1 in-depth interviews with 30 patients who originally accept, refuse, and are unsure about ICD implantation, for a total of 90 interviews. This sample size is expected to be sufficient to achieve thematic saturation in the qualitative data³¹. Patients participating in an in-depth interview will be purposively selected to ensure we collect a wide range of experiences from a diverse subset of individuals (e.g., education, gender, region, etc.). Round 2 interviews will be conducted (with their consent) with up to 60 participants who completed the first interview. The 30 individuals initially unsure about ICD implantation will be invited to complete a follow-up interview, to better understand what factors ultimately influenced their final decision. Additionally, any Round 1 interviewee whose 90-day ICD status differed from their 1-week decision (i.e., acceptors who did not have device implanted at 90 days and rejecters who did have device implanted at 90 days), will also be invited to complete an additional interview to understand factors that led to ultimate outcome.

The primary outcome will be the decision for ICD implantation at 7 days. Other outcomes include: the effect of racial concordance on the decision for ICD implantation, changes in patient knowledge (pre and post intervention), decisional conflict, and ICD receipt within 90 days of the decision for ICD implantation. The in-depth interviews will focus on: 1) knowledge of SCD and ICD therapy, 2) influences on the decision to accept or decline an ICD, 3) impact of the video on the decision (critique of the video content) 4) barriers to ICD placement following the initial decision. Lastly, study coordinators will assess the time spent with patients by providers in each arm of the study.

Analysis Plan: For the primary outcome, the proportion of patients saying “yes” to ICD will be compared between patients receiving the ICD video intervention (arms A + B) and patients receiving standard of care (arm C). The two proportions will be compared with the Pearson chi-square test. We do not expect small counts in light of the pilot study results but, if necessary, the Fisher Exact Test will be used. In addition to p-value we will provide estimates of proportions with their confidence intervals (exact confidence intervals will be used if needed).

EFFECT OF RACIAL CONCORDANCE

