We will use the DCS to measure decisional conflict. The scale measures a person's perception of the difficulty in making a decision, the extent to which they feel uncertain about treatment options, are knowledgeable about the risks and benefits of options, clear about personal values, and supported in decision making; the scale has demonstrated good reliability (Cronbach's alpha coefficients > 0.78) and predictive validity. Higher scores indicate greater decisional conflict and patients experiencing decisional conflict are more likely to change their minds, delay decisions, express regret, and fail knowledge tests. Patients will be administered the DCS *pre* intervention at the baseline enrollment visit, and post intervention, 1-week post enrollment. Respondents will be asked to reflect on their decision and respond to the DCS questions using a 5-point Likert scale. Responses to each statement are scored 0 (strongly agree) to 4 (strongly disagree). Total scores range from 0 to 100, with higher scores indicating greater decisional conflict. **Analysis Plan:** To determine differences in decisional conflict, each group's scores will be compared using independent samples t-test at two time points or Wilcoxon rank sum test if substantial departure from normality is noted. The first comparison will be within group (pre and post intervention) followed by 2) between group differences in the change scores using analysis of covariance (ANCOVA) that adjust for baseline scores. All quantitative tests will be two-sided and conducted at the 5% level of significance. Due to the secondary nature of these comparisons, there will be no adjustment for type I error. However, it is important to note that all these group comparisons are pre-specified and results of all attempted comparisons will be reported.

Sample size estimates:

In the pilot study, among black patients, the mean and standard deviation DCS scores for UC and video groups were 36.0 ± 3.2 and 33.7 ± 4.3 respectively. Based on these data and considering two-tailed equal variances t-test and 0.05 type I error, a sample size of 480 patients will have 99% power or higher for a mean DCS difference between arms of 3.0 across standard deviations of 2.5-5.0. For a mean difference between video and usual care arms equal to 1.0, SD 2.5, power remains at >99%.

ICD IMPLANTATION RATES

Compare the proportion of patients with an ICD implanted within 90 days of study enrollment in UC vs. combined video group.

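### The primary chi-square leaves out the ICD decision recorded before randomization; stratifying by it is a nearly free gain in power of uncertain size

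*SAP*

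**What the plan says.** **Primary test.** Under SAP 2.2, a "Pearson chi-square test will be used to test whether there is a difference in the proportion of patients accepting ICD implantation between combined video" and usual care groups, with Fisher's exact test as fallback and a difference in proportions with 95% CI. The protocol's analysis plan for the primary outcome agrees: "The two proportions will be compared with the Pearson chi-square test". Neither uses a baseline covariate. The only further evaluation named for this outcome is whether the effect differed before and after the CMS shared-decision rule.

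**Baseline answer.** The protocol's section on the DCS instrument states: "Prior to the intervention and at 1-week post intervention, participants will be asked to give their decision for ICD implantation (yes, no, unsure"). The DCS itself comes next. Appendix B opens with the item ("Which treatment option do you prefer"), offering ICD, no ICD or unsure.

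**Timing.** SAP 1.4 has patients complete the "knowledge questionnaire and the decisional conflict scale (DCS), on the iPad. The patient will then be randomized on the iPad". The protocol's enrollment section gives the same order.

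**Power.** SAP 1.5 works from 309 analyzable patients, 103 per arm, and usual-care acceptance of 43%. It states 91% power for a 20-point increase and "80% power to detect 17% absolute increase". It also records that, after enrollment difficulties, "a single primary comparison of video vs. usual care was chosen and type I error of 0.05 will be used".

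**Other outcomes.** Knowledge is analysed as a pre-to-post change. For the DCS the protocol plans to compare "between group differences in the change scores using analysis of covariance (ANCOVA) that adjust for baseline scores", while SAP 2.3.3 compares change scores with a t-test or Wilcoxon test.

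**The concern.** The pre-randomization answer is the outcome question itself, asked a week earlier, so it is likely to be among the strongest predictors of the 7-day answer that the trial collects. The secondary outcomes measured before and after the intervention use their baseline value in some form. The primary outcome does not.

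Precision matters here. The protocol planned to enroll 480 patients, whereas the SAP relies on 309 analyzable ones. The sponsor has already dropped a co-primary comparison and moved alpha from 0.025 to 0.05. At 309 patients the planned test has about 81% power for the 17-point pilot difference. For 15 points, the low end of the range that SAP 1.5 says could change practice, it has about 70%. Stratifying can add power without more patients, data or alpha. It also accounts for chance imbalance between arms in baseline preference.

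**Working it through.** **Inputs from the documents (SAP 1.5).** n0 = 103 (usual care), n1 = 206 (two video arms combined), p0 = 0.43, p1 = 0.60 (17 points) or 0.63 (20 points). Alpha is 0.05, read as two-sided because the earlier 0.025 is described as two-tailed.

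**Step 1: reproduce the stated power.** Let p̄ = (p0 + 2·p1)/3, SE0 = √[p̄(1−p̄)(1/103 + 1/206)] and SE1 = √[p0(1−p0)/103 + p1(1−p1)/206]. Then power = Φ[(p1 − p0 − z·SE0)/SE1].

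- 17 points: p̄ = 0.5433, SE0 = 0.0601, SE1 = 0.0595. (0.17 − 1.96 × 0.0601)/0.0595 = 0.877, so power is **81.0%** (stated: 80%).
- 20 points: p̄ = 0.5633, SE0 = 0.0599, SE1 = 0.0593. The argument is 1.396, so power is **91.9%** (stated: 91%).
- 15 points (p1 = 0.58): the argument is 0.535, so power is **70.4%**.
- 17 points at alpha 0.025 (z = 2.241): **72.3%**. The move to 0.05 therefore recovered about 9 points.

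**Step 2: assumptions for the stratified test.** The documents give neither the baseline split nor its association with the 7-day answer, so both were varied. Usual-care probabilities of a 7-day yes, by baseline yes/unsure/no, were:

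- none: 0.43/0.43/0.43
- weak: 0.58/0.38/0.26
- moderate: 0.68/0.33/0.17
- strong: 0.78/0.26/0.108

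For each split these were shifted on the logit scale so that the overall usual-care rate stayed at 43%. The video arm was a common odds-ratio shift to 60% overall. No shift is needed for the 40/35/25 split; for moderate association, 0.40 × 0.68 + 0.35 × 0.33 + 0.25 × 0.17 = 0.43.

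**Step 3: analytic cross-check.** If the baseline answer explains a share R² of outcome variance, the effective sample size is about 309/(1 − R²). For 40/35/25 with moderate association, R² = [0.40 × 0.25² + 0.35 × 0.10² + 0.25 × 0.26²]/(0.43 × 0.57) = 0.0454/0.2451 = 0.185. Scanning R² with the Step 1 formula gives the following power for 17 points:

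| R² | Effective N | Power |
|---|---|---|
| 0 | 309 | 81.0% |
| 0.10 | 343 | 84.9% |
| 0.20 | 386 | 88.8% |
| 0.30 | 441 | 92.4% |

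**Step 4: simulation.** There were 20,000 trials per cell (40,000 under the null), with 103 against 206 patients. Chi-square power was 80–81% in every cell. CMH power for 17 points was:

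| Baseline yes/unsure/no (%) | Weak | Moderate | Strong |
|---|---|---|---|
| 10/80/10 | 81.6% | 83.2% | 84.2% |
| 15/70/15 | 82.0% | 83.6% | 86.2% |
| 40/35/25 | 84.2% | 88.3% | 93.2% |
| 60/25/15 | 83.6% | 87.2% | 92.9% |

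- The 88.3% cell agrees with Step 3 at R² = 0.185, which lies between 86.8% (R² = 0.15) and 88.8% (R² = 0.20).
- With no association, CMH power was 80.5–80.7%, so there was no visible loss.
- For 15 points, 70% becomes 71–76% with the two mostly-unsure splits and 73–86% with the other two.
- Type I error was 0.048–0.051 for CMH and 0.046–0.051 for chi-square.
- The standard deviation of the risk difference was 0.059–0.060 unadjusted. With Mantel-Haenszel weighting it ran from 0.0592 (10/80/10, weak) to 0.0485 (40/35/25, strong), a reduction of about 1% to 18%.
- A separate simulation with different assumptions (30% yes, 30% no, 40% unsure) gave CMH power of 82.8%, 89.5% and 95.4% at R² of about 0.05, 0.21 and 0.37.

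**Step 5: does the remedy work in practice?** The Mantel-Haenszel risk-difference interval (Sato variance) covered 94.6–95.1% at 17 points and disagreed with the CMH p-value in about 0.3–0.4% of trials. This was checked on the first three splits in the Step 4 table. With 5% of baseline answers missing (assumed), a separate stratum for them cost at most 0.6 points of power. Dropping those patients cost 1.1–2.1 points. Where association was absent, or weak with mostly unsure patients, dropping them left power at 78–80%, below the plain chi-square.

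**The case against.** An unadjusted, pre-specified comparison of two proportions is legitimate in a randomized trial. The SAP's power claims are made at 17 and 20 points and both reproduce, so 70% at 15 points misses no stated target. This stands, and it is why the point is advisable rather than mandatory.

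The upper end of the gain rests on assumptions with no support in the documents. The baseline answer precedes the video or consultation. If most patients are then unsure, the gain is about 1 to 3 points with weak or moderate association and about 5 at most. The 60/25/15 split also requires acceptance under usual care to fall from 60% to 43% within a week. This stands as a caution on size. It does not change the choice, because the modelled downside is about zero. CMH also did not lose to chi-square when the video effect was confined to unsure patients.

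The contrast with ANCOVA for the DCS holds for the protocol only. SAP 2.3.3 plans no covariate adjustment, so within the SAP the primary outcome is not singled out.

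Pre-randomization capture is inferred by joining the protocol's statement that the decision is asked with the DCS to the order of events in SAP 1.4, which names only the DCS. The inference is sound but should be confirmed.

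Finally, a second late change to the primary analysis carries a credibility cost, and the documents do not show whether the window before unblinding is still open. A CMH analysis added only as a sensitivity analysis would avoid that cost but would leave the power of the primary test unchanged.

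**Conclusion.** The concern holds. The primary analysis omits a baseline measurement of the outcome question that the plan already collects before randomization. The chi-square is valid and the stated power is correct; what is lost is efficiency.

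At 309 patients and 17 points, the gain in the main grid is about 1 to 12 percentage points of power. It lies toward the low end if most patients are unsure at baseline, and nothing is lost if the baseline answer is uninformative. These figures rest on assumed baseline splits and associations, a common odds ratio for the video effect, and the SAP's rates of 43% and 60%. The change is worth making, but the trial is not unsound without it.

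**What to change.** Before data lock and unblinding, with the date recorded:

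1. Confirm that the decision item is captured on the iPad with the baseline DCS, before randomization.
2. In SAP 2.2, make the primary test a CMH test stratified by baseline decision (yes, unsure, no). Report the Mantel-Haenszel risk difference over the same strata with a 95% CI, so that test and interval match and the difference-in-proportions scale is kept.
3. Put missing baseline answers in their own stratum so that no patient is dropped.
4. Replace the Fisher fallback with an exact stratified test, and say whether the evaluation around the CMS rule is also stratified.
5. Keep the unadjusted chi-square as a sensitivity analysis.
6. Align the protocol's analysis plan for the primary outcome.

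The same adjustment in SAP 2.3.1 and 2.3.4 is optional. For concordant against discordant video (103 vs 103, 50% vs 70%), chi-square power is about 85% and CMH 83–95%, with about a 1-point loss if there is no association, so no gain is claimed there.

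The cost is wording in two documents and a few lines of code, with no new data. The primary comparison has already been changed once, so the timing must be documented. If unblinding has already happened, the stratified analysis should be supportive and the chi-square should remain primary.
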